#### **6.9 Months 15, 18, 21, 24, 27, 30, 33, and 36/End of Study (+/-1 month)**

Subjects will be evaluated every 3 months in Years 2 and 3 after SB-318 infusion.

An End of Study (EOS) visit will be conducted at Month 36.

At the EOS visit, subjects will be asked to participate in the LTFU Study. Study subjects may participate in the LTFU Study after 12 months of follow-up in this study, in which case an EOS visit may be conducted anytime after Week 52 but before the next scheduled study visit. Study participants who wish to enroll in the LTFU Study with less than 12 months of follow-up in this primary study may be considered on a case-by-case basis at the judgement of the Principal Investigator and after consultation with the Sponsor. In these cases an EOS visit may be conducted anytime when transition to the LTFU study is imminent. Informed consent will be obtained prior to participating in the LTFU Study.

The following assessments and procedures will be performed unless otherwise stipulated:

- Review and record concomitant medications.
- Physical examination.
- Vital signs.
- Assessment of AEs.
- ERT administration log.
- JROM (at Months 18, 24, 30, and 36/EOS only).
- Neurologic cranial nerve exam and muscle strength testing of the upper extremities (at Months 18, 24, 30, and 36/EOS only).

- 12-lead ECG (at Months 18, 24, 30, and 36/EOS only).
- ECHO (at Months 24 and 36/EOS only).
- Clinical laboratory tests.
- Liver panel.
- Chimerism assay (at Month 36/EOS only; for post-HSCT subjects only)
- GAG testing in urine.
- IDUA / GAG testing in blood.
- Circulating AFP level (at Months 18, 24, 30, and 36/EOS only).
- PFTs (at Months 18, 24, 30, and 36/EOS only).
- 6MWT (at Months 18, 24, 30, and 36/EOS only).
- Visual acuity test and corneal clouding exam (at Months 24 and 36/EOS only).
- Neurocognitive abilities tests by WASI-II, WPPSI-IV, or BSID-III, and by VABS-II (at Months 18, 24, 30, and 36/EOS only).
- MRI of liver (at Months 18, 24, 30 and 36/EOS only).
- MRI of brain and cervical spine (at Months 24 and 36/EOS only).
- Immunogenicity assays (at Months 18 and 24 only).

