## 6.10 Early Termination

Subjects who discontinue from the study prematurely or are withdrawn from the study will be asked to return to the study site for an Early Termination visit (ETV).

It is at the discretion of the Principal Investigator, in consultation with the Medical Monitor, to waive any procedure if the procedure has been performed within the standard interval of scheduled study visits per protocol.

The following assessments and procedures will be performed:

- Review and record concomitant medications.
- Physical exam.
- Vital signs.
- Assessment of AEs.
- ERT administration log.
- JROM.
- Neurologic cranial nerve exam and muscle strength testing of the upper extremities.
- 12-lead ECG.
- ECHO.
- Clinical laboratory tests.

- Liver panel.
- Chimerism assay.
- GAG testing in urine.
- IDUA / GAG testing in blood.
- Circulating AFP level.
- PFTs.
- 6MWT.
- Visual acuity test and corneal clouding exam.
- Neurocognitive abilities tests by WASI-II, WPPSI-IV, or BSID-III, and by VABS-II.
- MRI of liver.
- MRI of brain and cervical spine.

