Visual Acuity Test & Corneal Cludging Exam		X											X					X			X				X	X
VABS-II	X	X											X					X			X	X	X	X	X	X
Neurocognitive Abilities Assessment	X																									
Neurocognitive Abilities Testing (k)		X											X					X			X	X	X	X	X	X
MRI of Liver	X												X					X			X	X	X	X	X	X
MRI of Brain and Cervical Spine (l)		X																X					X			X
ACTH Stimulation (Cosyntropin) Test (m)		X (prior to prednisone)											X													
Liver Biopsy (n)		X											X					X								
Lumbar Puncture (n)		X												X					X							
Immunogenicity Assays (o)		X							X	X			X			X		X			X	X				
Prednisone (or equivalent corticosteroid) Administration (p)		X	X						X																	
SB-318 Infusion			X																							

\* Week 28, 32, 40, 44, and 52 study visits have assessments that do not require evaluation at the clinical site, and therefore may be conducted remotely. Blood and urine samples at these visits may be collected by a qualified home health nurse. For these study visits, GAG testing in urine may be waived for subjects who do not reside in the U.S. Assessments for AEs, concomitant medications and ERT administration log may be conducted remotely over the phone by study staff.

§ Study subjects may participate in the LTFU Study after 12 months of follow-up in this study, in which case an EOS visit may be conducted any time after Week 52 but before the next scheduled study visit. Study participants who wish to enroll in the LTFU Study with less than 12 months of follow-up in this primary study may be considered on a case-by-case basis at the judgement of the Principal Investigator and after consultation with the Sponsor. In these cases, the EOS visit may be conducted at any time on this study.

- Vital signs (height, weight, systolic/diastolic blood pressure, heart rate, respiratory rate, and temperature; for frequency, refer to the Study Reference Manual.
- As permitted by subject's capacity.
- Serum pregnancy test will be performed at Screening and Baseline visits. Urine pregnancy test will be performed on the Day 0 visit if >7 days from Baseline pregnancy test. Urine pregnancy tests will be performed until Week 48 or until 3 consecutive plasma samples are negative for AAV2/6, whichever occurs first.
- Liver panel does not need to be drawn as a separate sample if samples for Clinical Laboratory Tests are obtained at the same visit.

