In this study, the objective and rationale for the proposed SB-318 investigational therapy is to abrogate or decrease the need for ERT using *in vivo* genome editing. The proposed treatment employs recombinant adeno-associated virus (rAAV) comprising engineered zinc finger nucleases (ZFNs) to site-specifically integrate a corrective copy of the human iduronidase enzyme (hIDUA) transgene into the genome of subjects' own hepatocytes *in vivo*. Integration of the hIDUA transgene is targeted to intron 1 of the albumin locus, resulting in stable, high level, liver-specific expression and secretion of hIDUA into the blood. Placement of the hIDUA transgene under the control of the highly expressed endogenous albumin locus is expected to provide permanent, liver-specific expression of hIDUA for the lifetime of an MPS I patient.

The purpose of the Statistical Analysis Plan (SAP) is to describe the analyses and data presentations for Sangamo's protocol SB-318-1502 (Amendment version 7). This SAP outlines the types of analyses that will address the study objectives and explains in detail how the data will be handled and analyzed. It contains the definitions of analysis sets and statistical methods for the analysis of endpoints. Since this is an exploratory Phase I study, all analyses will be descriptive and exploratory in nature. No hypotheses testing will be carried out.

2. Objectives

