3.4. Dose Modifications

No dose modifications are possible within an individual subject since this is a single infusion study.

4. General Statistical Considerations

Study days will be numbered relative to the date of SB-318 infusion. For assessments on or after the date of SB-318 infusion, the study day of events from SB-318 infusion is calculated as the date of event minus the date of infusion. For assessments prior to the date of SB-318 infusion, the study day of events from SB-318 infusion is calculated as the date of event minus the date of infusion. Thus, the study day of event before the date of the infusion will be negative number, and the study day of the date of infusion will be 0.

Baseline is defined as the last non-missing measurement prior to the SB-318 infusion. Where only date is available, the date of the collection must be prior to the date of SB-318 infusion. Where time is also available, the time of the collection must be prior to the time

of SB-318 infusion. For example, for vital signs parameters, measures that are taken at the latest time prior to the infusion will be defined as baseline values. Measurements that are obtained after infusion will be considered as post-baseline values. If the measurement of a variable is not made on a given subject prior to infusion, then that subject will be considered not to have a baseline value for that variable. Change from baseline is defined as post-baseline assessment minus baseline assessment.

Continuous data will be summarized using the following descriptive statistics: number of subjects (n), mean, standard deviation (SD), median, minimum and maximum, where appropriate. Categorical data will be summarized using the frequency count (n) and percentage (%) of subjects for each category, where appropriate.

Unless specified otherwise, all the summary tables will be presented by treatment cohort and overall, and all the collected data will be presented in the listings, and data displayed in the listings will be sorted by treatment cohort and subject identifier.

No imputation will be applied for missing data unless otherwise specified.

All analyses will be conducted using SAS® Version 9.3 or later. The Medical Dictionary for Regulatory Activities (MedDRA 23.0) will be used for coding adverse events.

Concomitant medication data will be coded using the World Health Organization (WHO) Drug Dictionary.

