5.1. Disposition

A disposition of subjects includes the number and percentage of subjects for the following categories: subjects who screen failed, subjects who were enrolled, subjects who received any portion of the SB-318 infusion, subjects who completed the study, and subjects who terminated early from the study. The disposition will be summarized by treatment cohort and overall. The percentages will be based on the number of subjects in each treatment cohort and overall. The reasons for early termination of study will also be summarized in the table.

Subject disposition data will be presented in a listing. A separate listing of reasons for screen failure will be provided. The number of screen fails and the screen criteria failed will be summarized in a table.

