8.1. Primary Endpoint Analysis

8.1.1. Adverse Events

A treatment-emergent adverse event (TEAE) is defined as any adverse event with an onset date on or after the date of the SB-318 infusion through the last study visit, whether or not it is considered causally related to the study drug.

Treatment Emergence:

Totally Missing Dates:

- If both the onset date and the end date are, then the adverse event is assumed to be treatment emergent.

Partially Missing Dates:

- If the onset date is missing and the non-missing end date is prior to the infusion date, then the AE is not considered treatment emergent.
- If the partial end date can be assumed to be prior to the infusion date (month and/or year before infusion date), then the AE is not considered treatment emergent.
- If the end date is after the infusion date or the partial end date can be assumed to be on or after the infusion date (based on month and/or year), then the AE is assumed to be treatment emergent.
- If the onset date is partial and can be assumed to be prior to the infusion date (based on the month and/or year) or the non-missing end date is prior to the infusion date then the AE is not considered treatment emergent.
- If the partial onset date can be assumed to be on or after the infusion date, then the AE is assumed to be treatment emergent.

All AEs will be coded according to the most recent version of the MedDRA. Severity will be categorized by toxicity grade according to the Common Terminology Criteria for Adverse Events (CTCAE) Version 4.03.

AEs not listed in the CTCAE version 4.03 will be evaluated by using the following criteria:

- Grade 1, Mild: Symptoms cause no or minimal interference with usual social and functional activities
- Grade 2, Moderate: Symptoms cause greater than minimal interference with usual social and functional activities
- Grade 3, Severe: Symptoms cause inability to perform usual social and functional activities

- Grade 4, Potentially Life-threatening: Symptoms cause inability to perform basic self-care functions OR medical or operative intervention indicated to prevent permanent impairment, persistent disability, or death
- Grade 5: Outcome of AE is death.

Incidence of Adverse Events

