SB-318 5.00E+13 vg/kg	XXXXXX	XXX	XXX	XXX

Source Data: Listing 16.2.4.2

<DIRECTORY PATH>PROGRAM NAME Executed: DDMMYYYY hh:mm

Table 14.2.1
Change from Baseline in Plasma and Leukocyte IDUA Activity
Safety Set

Parameter: Alpha Iduronidase Plasma (nmol/hr/mL)

Visit	SB-318 1.00E+13 vg/kg (N=xx)		SB-318 5.00E+13 vg/kg (N=xx)		Total (N=xx)	
	Actual Value	Change From Baseline [1]	Actual Value	Change From Baseline [1]	Actual Value	Change From Baseline [1]
BASELINE						
n	xx		xx		xx	
MEAN (SD)	xx.x (xx.xx)		xx.x (xx.xx)		xx.x (xx.xx)	
MEDIAN	xx.x		xx.x		xx.x	
MIN, MAX	xx, xx		xx, xx		xx, xx	
VISIT X						
n	xx	xx	xx	xx	xx	xx
MEAN (SD)	xx.x (xx.xx)	xx.x (xx.xx)	xx.x (xx.xx)	xx.x (xx.xx)	xx.x (xx.xx)	xx.x (xx.xx)
MEDIAN	xx.x	xx.x	xx.x	xx.x	xx.x	xx.x
MIN, MAX	xx, xx	xx, xx	xx, xx	xx, xx	xx, xx	xx, xx

..
Note: Baseline is defined as last non-missing measurement prior to dosing.

[1]Change from baseline: post-baseline value - baseline value. For the change from baseline, only subjects with a value at both baseline visit and the specific post-baseline visit are included.

Source Data: Listing 16.2.9.3

<DIRECTORY PATH>PROGRAM NAME Executed: DDMMYYYY hh:mm

Prog Notes: Repeat for Alpha Iduronidase Leukocyte (nmol/hr/mL) parameter. Post baseline visits include Day 7, Weeks 2, 4, 6, 8, 12, 16, 20, 24, 36, 48, Months 15, 18, 21, 24, 27, 30, 33, 36/ EOS, or Early Termination Visit if applicable.

Table 14.2.2
Change from Baseline in Urine GAG Levels and Urine GAG/Creatinine Ratio
Safety Set

Parameter: Total Glycosaminoglycans (GAGs) (mg/mmol creatinine)

Visit	SB-318 1.00E+13 vg/kg (N=xx)		SB-318 5.00E+13 vg/kg (N=xx)		Total (N=xx)	
	Actual Value	Change From Baseline [1]	Actual Value	Change From Baseline [1]	Actual Value	Change From Baseline [1]
BASELINE						
n	xx		xx		xx	
MEAN (SD)	xx.x (xx.xx)		xx.x (xx.xx)		xx.x (xx.xx)	
MEDIAN	xx.x		xx.x		xx.x	
MIN, MAX	xx, xx		xx, xx		xx, xx	
VISIT X						
n	xx	xx	xx	xx	xx	xx
MEAN (SD)	xx.x (xx.xx)	xx.x (xx.xx)	xx.x (xx.xx)	xx.x (xx.xx)	xx.x (xx.xx)	xx.x (xx.xx)
MEDIAN	xx.x	xx.x	xx.x	xx.x	xx.x	xx.x
MIN, MAX	xx, xx	xx, xx	xx, xx	xx, xx	xx, xx	xx, xx

...
Note: Baseline is defined as last non-missing measurement prior to dosing.

[1]Change from baseline: post-baseline value - baseline value. For the change from baseline, only subjects with a value at both baseline visit and the specific post-baseline visit are included.

Source Data: Listing 16.2.9.4

<DIRECTORY PATH>PROGRAM NAME Executed: DDMMYYYY hh:mm

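### The SAP's combined Month 36/EOS row has no rule for EOS visits held at early roll-over to the LTFU study, so early values could be averaged with true Month 36 values (minor)

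*SAP*

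**What the plan says.** Protocol Section 6.9 sets the EOS visit at Month 36, with a window of one month either side. It also allows entry to the LTFU study after 12 months of follow-up, "in which case an EOS visit may be conducted anytime after Week 52 but before the next scheduled study visit". Entry before 12 months is possible case by case, and the footnote to the schedule in Appendix 1 adds: "In these cases, the EOS visit may be conducted at any time on this study". The Early Termination visit is a different visit with a different trigger. Section 6.10 says: "Subjects who discontinue from the study prematurely or are withdrawn from the study will be asked to return to the study site".

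In the SAP, the programming note to shell Table 14.2.1 ends its visit list with "Months 15, 18, 21, 24, 27, 30, 33, 36/ EOS, or Early Termination Visit if applicable". Fourteen other shells carry the same combined Month 36/EOS entry. The note to Table 14.3.4.2 (serum chemistry) asks for every post-baseline visit without naming any. SAP Section 4 defines study day, baseline and change from baseline. On later values it says only: "Measurements that are obtained after infusion will be considered as post-baseline values". The available SAP text does not mention the LTFU study, early roll-over or analysis windows.

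**The concern.** A row in a by-visit table is read as a time point. Here one row label covers two kinds of visit that the protocol allows to be far apart. The protocol names the roll-over visit EOS and ties Early Termination to premature discontinuation or withdrawal. A programmer following the shells therefore has an obvious place for a roll-over EOS, which is the row that also holds Month 36.

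At stake is the last row of the IDUA, urine GAG, functional and safety tables. Protocol Section 1.7 expects permanent expression of the enzyme, so this is the row in which a reader would look for durability. Cohorts are very small, so one displaced value carries real weight. Without a rule, two programmers working from the same SAP could also produce different last rows.

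**Working it through.** The plan states no figure to reproduce. The check sets the protocol's visit rules against the shells and then does calendar and weighting arithmetic.

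**Where a roll-over visit would go**

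| Situation | Name in the protocol | Row in the shells |
|---|---|---|
| Month 36 reached | EOS | 36/EOS |
| Roll-over after 12 months | EOS | 36/EOS, if recorded as EOS |
| Roll-over before 12 months, case by case | EOS | 36/EOS, if recorded as EOS |
| Premature discontinuation or withdrawal | Early Termination visit | Early Termination |

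**How many tables.** The combined entry is in Tables 14.2.1, 14.2.2, 14.2.4 to 14.2.8, 14.3.4.1, 14.3.4.3 and 14.3.5 to 14.3.10: 2 + 5 + 2 + 6 = 15. Table 14.3.4.2 has no visit list and needs the same rule, which makes 16.

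**Gap in timing.** One month is 365.25/12 = 30.44 days.
- The Month 36 window opens at Month 35: 35 × 30.44 = Day 1065.
- EOS just after Week 52: 52 × 7 = Day 364. Gap: 1065 − 364 = 701 days, or 23.0 months.
- EOS just before nominal Month 15: 15 × 30.44 = Day 457. Gap: about 609 days, or 20.0 months.
- The Section 6.9 wording can also be read as allowing an EOS between any two later visits. The gap could then shrink to a few months or less.
- Roll-over before Month 12 has no stated lower limit, so the gap could exceed 23 months.

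**Weight of one early value.** Assume exactly one early roll-over, recorded as EOS, with all other subjects reaching Month 36. In a row of n subjects the mean shifts by

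shift = (value at early EOS − the same subject's value had it been taken at Month 36) / n,

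which is zero if the measure is stable. Sizes come from the cohort table in SAP Section 3.1 (1 subject in Cohort 1, 2 in Cohort 2) and from the option in Protocol Section 11.1 of about 2 more subjects in any cohort. The Total refers to the two dose columns in the shells.

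| Row | n as planned | Share | n if expanded | Share |
|---|---|---|---|---|
| Cohort 2 | 2 | 1/2 (50%) | 4 | 1/4 (25%) |
| Total, Cohorts 1 and 2 | 3 | 1/3 (33%) | 3 + 4 = 7 | 1/7 (14%) |

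**Would the tables show it?** A subject who leaves soon after Week 52 lowers n in the rows from Month 15 to Month 33, and n rises again at 36/EOS. Of the 15 shells, 11 have three or more such rows, three have one (WASI-II, vision and cornea, echocardiogram), and one has none (chimerism).

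**The case against.** The harm needs two things that the documents do not show: at least one early roll-over, and a CRF that records the visit as EOS. If it is recorded as Early Termination, no row is shared. This stands, and the point is conditional for that reason.

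The label comes from Protocol Section 6.9, and it tells the reader that the row may hold an EOS value. SAP Section 8.2.1 speaks only of an end of study visit, and the shells print a generic visit placeholder. The combined row is therefore inferred from the programming notes. This also stands. It rules out calling the label misleading when a cohort has one subject, but it supplies no rule for separating the two kinds of visit.

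The information is not lost. Listing 16.2.1.1 gives each subject's completion or termination day, and the result listings give dates and study days. With cohorts this small, many readers will go to the listings first. The SAP also states: "No hypotheses testing will be carried out". Chimerism, the least transparent table, applies only to subjects with a prior transplant, and the documents do not show that any were enrolled. These facts limit the severity. They do not repair the summary tables.

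A reader might infer that unequal follow-up in the adverse-event tables is part of the same defect, since events are counted "on or after the date of the SB-318 infusion through the last study visit". Follow-up of 12 against 36 months would be a 3-fold difference. It would arise from any early exit, however the EOS row is built, so it is a separate reporting matter. The same holds for disposition: SAP Section 5.1 counts "subjects who completed the study, and subjects who terminated early from the study" without placing roll-over subjects in either group, but that does not affect the visit rows.

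**Conclusion.** The point holds as a minor defect of the summary tables. In a situation the protocol foresees, following the shells literally would put a roll-over EOS value in the same row as Month 36 values, and nothing in SAP Section 4 prevents it. The timing gap runs from a few months or less to about 23 months, and further for roll-over before Month 12. The share of the row depends on there being exactly one early roll-over and on cohort size: 1/2 to 1/4 in Cohort 2, and 1/3 to 1/7 in the Total. The effect on a mean also depends on how far that subject's value would have changed by Month 36, which is unknown and may be nothing.

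A reader might go further and conclude that the final efficacy and safety rows will be mixed, or that half of a row will be early data. The documents do not support that. They give no count of early roll-overs and do not show the CRF coding, and the one-half share belongs only to an unexpanded cohort of 2.

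**What to change.** Add a short visit-assignment rule to SAP Section 4 and apply it to the 15 shells and to Table 14.3.4.2:
- The Month 36 row holds only visits inside the Month 36 window (one month either side) and nominal Month 36 visits held late.
- EOS visits at roll-over before that window are not averaged into the Month 36 row or with each other. They are shown by subject with study day.

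The second rule matters because one pooled row for early EOS visits would again mix times, from before Month 12 to nearly Month 35.

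The cost is one SAP paragraph and edits to the programming notes. The by-subject display is needed only if an early roll-over occurs. Data collection does not change. The downside is a smaller n in the Month 36 row.

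Two optional additions would help the reader but are separate from this defect: a line for roll-over to the LTFU study in Table 14.1.1.1, with a statement in SAP Section 5.1 on whether such subjects count as completed, and a summary of follow-up duration by cohort beside the treatment-emergent adverse event tables.
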